Obstructive Sleep Apnea in Pregnancy:
Development of a Pregnancy-Specific Screening Tool

NCT02383706

Document Date: August 1, 2018

This study was approved by the Duke University Medical System Institutional Review Board and registered in ClinicalTrials.gov (NCT02383706). We prospectively enrolled adult pregnant, nulliparous and multiparous subjects, between 24 and 35 weeks gestation from a university-affiliated prenatal clinic. Women were included if they had a BMI ≥ 40 kg.m⁻² at the time of enrollment and were 18 years or older. The World Health Organization classification of obesity was utilized to define class 3 (extreme) obesity.¹ Women with an established diagnosis of OSA or chronic opiate use, and subjects who did not speak English were excluded.

Following informed consent, demographic data was recorded (including pre-pregnancy BMI from chart review) and subjects completed three sleep disordered breathing screening questionnaires: the Berlin² (BQ) and STOP-BANG^{3,4} questionnaires, and the American Society of Anesthesiologists' (ASA) checklist.⁵ Subjects also completed the Epworth Sleepiness Scale (ESS) which is used to assess sleepiness that can be associated with OSA.⁶ An OSA risk score was also calculated for each subject using the method proposed for use in pregnant women by Facco *et al.*²

$$\text{OSA risk score} = \text{Age} + \text{BMI}_{\text{pre-pregnancy}} + 15 \text{ (if frequent snoring)} + 15 \text{ (if chronic hypertension)}$$

The BQ, STOP-BANG, and ASA questionnaires, as well as the ESS were scored using published methods.^{2,5-7} The BQ contains 10 items classified into three categories: Category 1 concerns snoring; Category 2 concerns daytime sleepiness; and Category 3 relates to BMI > 30 kg.m⁻² and chronic hypertension. The BQ is considered high risk for OSA if two of three categories were scored as positive.² Similarly, the ASA checklist contains 12-items in three categories: clinical signs and symptoms; history of apparent airway obstruction during sleep; and somnolence. If 2 or more of these categories are

endorsed, the patient is considered at high risk for OSA.⁵ Each item on the STOP-BANG questionnaire receives one point, with the highest total possible score in this cohort equal to 6 (as male gender and age greater than 50 years do not apply to any of the subjects).^{7,8} The ESS is considered concerning for excessive daytime sleepiness if scores are in the 11-24 range.⁶

Study data were entered into and managed using REDCap electronic data capture tools hosted at Duke University. REDCap (Research Electronic Data Capture) is a secure, web-based application designed to support data capture for research studies, providing: 1) an intuitive interface for validated data entry; 2) audit trails for tracking data manipulation and export procedures; 3) automated export procedures for seamless data downloads to common statistical packages; and 4) procedures for importing data from external sources.⁹

Vital signs were recorded, and subjects underwent a physical examination of the neck and upper airway by trained research assistants in the Department of Anesthesiology to measure neck circumference⁴ and thyromental distance, and to assess retrognathia, tongue scalloping¹⁰, Mallampati score (MMS)¹¹, modified MMS¹², tonsil size and lateral pharyngeal wall narrowing. MMS is a 1-4 numerical rating system commonly used to assess the airway and predict difficulty of intubation that is assessed by asking the subject to open their mouth as wide as possible with the tongue protruding. The modified Mallampati score leaves the tongue inside the mouth. Neck circumference was measured using a disposable measuring tape at the midpoint of the

neck just below the thyroid cartilage. Thyromental distance was measured using a disposable paper measuring tape from the mandible to the top of the thyroid cartilage. Retrognathia, tongue scalloping, MMS, modified MMS, tonsil size and lateral pharyngeal wall narrowing were rated using an illustrated numerical scoring tool.

Subjects received an unattended type III home sleep apnea test (ApneaLink Air™, ResMed, Poway, CA, USA), and instructions for wearing it during one night of sleep. The home sleep test consists of a pulse oximeter for recording of oxygen saturation and heart rate, a respiratory effort belt for measurement of respiratory effort, and a nasal sensor for detection of flow limitation, apnea hypopnea index (AHI) and snoring. The software on the device calculates AHI from the sum average number of apneas (80%-100% reduction in airflow with respiratory effort ≥ 10 seconds) and hypopneas (50%-80% reduction in airflow with respiratory effort ≥ 10 seconds) per hour during the recording time, based on the standard definitions of the American Academy of Sleep Medicine. The software also generates a report with details regarding variation in oxygen saturation during the study. Subjects with an AHI greater than 5 per hour on the home sleep test were referred to a sleep medicine physician for further evaluation.

Pregnancy outcomes were followed for all subjects, including maternal death, gestational diabetes, cerebrovascular accident, spontaneous labor, induction of labor, oxytocin administration during labor, cesarean delivery, estimated blood loss, neonatal weight, and composite outcomes of adverse maternal cardiovascular and peripartum events, and adverse fetal outcomes. A composite adverse maternal cardiovascular

outcome combined cases of: gestational hypertension; mild and severe preeclampsia; eclampsia; cardiomyopathy; and congestive heart failure. A composite adverse peripartum outcome included cases of: postpartum hemorrhage; maternal ICU admission; and post-operative wound infections. A composite adverse fetal outcome included cases of: neonatal intensive care unit admission; fetal growth restriction; preterm delivery (< 37 weeks gestation); and fetal demise.

Statistical analysis

OSA outcome was defined as $AHI \geq 5$ events per hour among patients with at least 2 hours of nasal air flow time recorded. This measure was chosen to assess outcome because it represents the threshold for referral for in laboratory PSG and an OSA screening measure will need to be able to sensitively and specifically indicate when a referral for PSG is needed. We summarized the patient demographic, physical, and clinical characteristics as well as questionnaire responses in each outcome group via mean (SD) or median (Q1, Q3) for numeric variables and N (%) for categorical variables. We assessed univariate associations of patient characteristics and questionnaire responses with OSA outcome via t-test or Wilcoxon rank sum test for numeric variables, and chi-square or Fisher exact test for categorical variables.

We assessed the performance and agreement of the previously defined OSA risk scores via receiver operating curve (ROC) area under the curve (AUC) analysis, logistic regression, and Kendall Tau correlation for the numeric scores, and via sensitivity and

specificity, net reclassification indices (NRI) and Kappa statistics for the binary risk stratification.

We designed the study with an expectation of an OSA positive rate of 30-40% in our high-risk population.^{1,2} A study of 80 patients (24-32 with OSA) with completed valid home sleep test, achieves 79% power in a logistic regression with two-sided $\alpha=0.05$ to detect an odds ratio of 2.5 for a numeric risk score when the OSA rate is 35%. For the Kappa statistic used to assess agreement, with 80 subjects and an OSA rate of 35%, we will achieve 82% power at $\alpha = 0.05$ to detect the difference between a kappa of 0.45 (fair agreement) and 0.75 (strong agreement). Power and sample size calculation were performed in NQuery (Statistical Solutions Ltd) software, statistical analysis was performed in SAS v9.4 (SAS Inc., Cary, NC), and significance was set at 0.05 level.

1. Obesity: preventing and managing the global epidemic. Report of a WHO consultation. *World Health Organ Tech Rep Ser.* 2000;894:i-xii, 1-253.

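### The AHI is stated per hour of an undefined recording time, while validity is judged on nasal flow time; if the two differ, some women with partial flow loss are classed OSA-negative

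*Combined protocol and SAP*

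**What the plan says.** The paragraph on the home sleep apnea test (unnumbered, before the Statistical analysis heading) describes an unattended three-sensor device, given with "instructions for wearing it during one night of sleep". The sensor that supplies the AHI is "a nasal sensor for detection of flow limitation, apnea hypopnea index (AHI) and snoring". Apneas and hypopneas are both defined there as reductions in airflow, and the device software averages them "per hour during the recording time, based on the standard definitions".

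The Statistical analysis section defines OSA as an AHI of 5 or more "events per hour among patients with at least 2 hours of nasal air flow time recorded". The sample size counts only such tests: "A study of 80 patients (24-32 with OSA) with completed valid home sleep test".

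The document does not define recording time or give its length. It sets no minimum share of the recording that must contain flow, and it describes no rescoring or correction for lost signal.

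**The concern.** The numerator of the AHI can grow only while the nasal sensor delivers a signal. The validity rule respects this, because it counts flow hours. The denominator uses a different term. If that term covers hours when the belt and oximeter were running but the nasal signal was lost, those hours add to the denominator and cannot add events.

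Such an error runs one way: it can turn a positive into a negative, never the reverse. The effective cut-off would also differ between women according to signal quality, so an AHI of 5 would not mean the same thing for all of them. This AHI is the reference outcome for the univariate comparisons, the ROC and logistic analyses, and sensitivity, specificity and NRI, with only 24 to 32 cases expected.

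**Working it through.** **1. The plan's own figure.** The plan says the design "achieves 79% power in a logistic regression with two-sided" alpha 0.05, for n = 80, odds ratio 2.5 and OSA rate 35%. I take the odds ratio as per SD of the score (an assumption) and use the Hsieh 1989/Whittemore formula for one normal covariate:

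power = Phi[(sqrt(n p b²/(1 + 2 p d)) - 1.96)/exp(-b²/4)], with d = [1 + (1 + b²) exp(5b²/4)]/[1 + exp(-b²/4)]

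- b = ln 2.5 = 0.916, b² = 0.840, d = 3.454
- n p b² = 23.51; 1 + 2 p d = 3.418; square root of the ratio = 2.623
- (2.623 - 1.96)/0.811 = 0.817, giving power 79.3%

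This reproduces the stated 79%, which is not in dispute.

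**2. Effect of the denominator.** Let A be the AHI per flow hour, F the flow hours and T the recording hours. The events counted are A x F. If recording time is total device time:

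reported AHI = A x F/T, so the reported AHI is at least 5 only when A is at least 5 x T/F

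The documents give no T, so the values below are assumptions. The 2 hours is the plan's minimum.

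| F (h) | T = 4 h | T = 6 h | T = 7 h | T = 8 h |
|---|---|---|---|---|
| 2 | 10 | 15 | 17.5 | 20 |
| 4 | 5 | 7.5 | 8.75 | 10 |
| 6 | n/a | 5 | 5.8 | 6.7 |

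Entries are the AHI per flow hour needed to be classed OSA-positive.

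Two examples at F = 2 h, T = 7 h:
- A = 10: 20 events, 20/7 = 2.9 per hour, classed negative.
- A = 20: 40 events, 40/7 = 5.7 per hour, still positive.

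Women with A below 5 stay negative under either denominator.

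**3. Share of positives lost among women with partial flow (illustration).** Assume a lognormal A with 35% at or above 5, log-SD s from 0.8 to 1.2, and flow loss unrelated to A. Then:

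share lost = 1 - [1 - Phi(0.385 + ln(T/F)/s)]/0.35

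For F/T = 0.7 and s = 1.0: 0.385 + 0.357 = 0.742, upper tail 0.229, and 1 - 0.229/0.35 = 35%.

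| F/T | s = 0.8 | s = 1.0 | s = 1.2 |
|---|---|---|---|
| 2/7 | 93% | 86% | 78% |
| 4/7 | 60% | 51% | 44% |
| 0.70 | 42% | 35% | 29% |
| 0.85 | 21% | 17% | 14% |

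**4. Effect on the whole cohort.** The number of women with partial flow is not given, so these are scenarios:
- 10% of 80 women at 70% flow: 8 x 0.35 = 2.8 cases, of which 0.8 to 1.2 are missed. If 20%, 1.6 to 2.4.
- 5%, 10% or 20% of women with only 2 of 7 hours: 1.1 to 1.3, 2.2 to 2.6, or 4.4 to 5.2 missed. Power by the formula in step 1, at the lower observed rate, is about 79%, 78% or 76-77%. This counts the rate effect only, not any dilution of the odds ratio.

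**5. Accuracy measures (illustration).** Take 28 cases in 80 and a tool with sensitivity and specificity of 80%. Move 4 cases to the negative group, independently of the tool's result. Observed prevalence is 24/80 = 30%. Test-positives among the 56 labelled negative are 0.2 x 52 + 0.8 x 4 = 13.6, so apparent specificity is 42.4/56 = 76%.

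**The case against.** The strongest reply is that the premise is not written down. Recording time may mean the hours of flow recorded, since the Statistical analysis section itself speaks of flow time as recorded. The listed sensors include no channel that stages sleep, so the phrase may only signal that the denominator is not sleep time. The software's formula is not shown. If it divides by flow hours, no one is misclassified and one sentence is badly worded. This stands, and makes the misclassification conditional. Total device time remains the plainer reading, because the plan had a term for flow time and used a different one for the denominator.

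The reply is also right on size. Two hours is a minimum, not a typical night, and the larger percentages in step 3 apply only to true positives with that degree of loss.

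A reader might further infer that AUC, odds ratios and kappa are all attenuated. The documents do not support this. If the flow share were similar in all women, the result would be a higher effective threshold, which need not lower AUC or sensitivity. Attenuation requires flow loss to be unrelated to the scores, and that is not stated. The kappa and Kendall Tau analyses may compare the tools with one another, in which case the AHI does not enter.

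**Conclusion.** The concern holds in a conditional form. The denominator of the reference outcome is undefined and does not match the quantity used for validity. If it is total device time, women with partial signal loss and an AHI per flow hour from 5 to below 5 x T/F are classed OSA-negative. At the minimum of 2 flow hours the effective cut-off is 10 to 20 per hour for an assumed T of 4 to 8 h. Observed prevalence would then be too low. How sensitivity, specificity and AUC move depends on how flow loss relates to the scores.

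It would be wrong to conclude that every woman who lost the nasal signal is misclassified, or that misclassification is established. Those below 5 and those at or above 5 x T/F keep their class. With recording length and the number of women with partial flow both unreported, the net effect may be small: about one to five cases across most of the scenarios in step 4. Under either reading, the reference outcome cannot be reproduced from the text as written.

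**What to change.** - Define the outcome AHI as apneas plus hypopneas divided by hours of evaluable nasal flow, the same quantity as the 2-hour validity rule.
- Confirm from the device software that this is how the reported AHI is formed. If it is not, recompute it from the stored device reports and use it in every analysis that involves OSA status.
- Report the distribution of flow hours and recording hours among the valid tests, and give the recording-time AHI as a sensitivity analysis.
- If the software already divides by flow time, correct the sentence on recording time; no reanalysis is then needed.

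The cost is one sentence and, at most, a small recalculation from stored device reports. The OSA rate may rise slightly.
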